3.5. Manufacturing & Distribution of Product

Investigational products (including active treatments and placebo) for this study will be manufactured and distributed to participants by Vitazan Herbs and Supplements Inc. Specific formulations of each study product are outlined below.

Specific Product: Vitamin D3 50,000 IU

Formulation: Capsule. Each capsule will contain 500 mg (50,000 units) cholecalciferol (vitamin D3)

Dose: One capsule on day 1 of the intervention period

Placebo Equivalent: microcrystalline cellulose capsule, 350 mg

Absolute Contraindications: history of hypervitaminosis D, hypercalcemia or sarcoidosis

Specific Product: Vitamin K2/D

Formulation: Liquid. Each 0.0285 mL drop contains 30 mcg menaquinone-7 (MK-7, vitamin K2) and 3.125 mcg (125 units) cholecalciferol (vitamin D3).

Dose: 0.114 mL (four drops) twice daily for 21 days totalling 240mcg MK-7 and 1,000 units cholecalciferol per day.

Placebo Equivalent: Medium chain triglyceride oil

Absolute Contraindications: history of hypervitaminosis D, hypercalcemia or sarcoidosis; warfarin or another vitamin K antagonist anticoagulant

Specific Product: Vitamin C/Zinc

Formulation: Capsule. Each capsule will contain 666 mg ascorbic acid (vitamin C) and 8.3 mg of zinc acetate

Dose: Three capsules three times daily for 21 days totalling 6 g ascorbic acid and 75 mg zinc acetate per day.

Placebo Equivalent: microcrystalline cellulose capsule, 350 mg

Absolute Contraindications: calcium oxalate kidney stones, end stage chronic kidney disease, cephalexin, tetracycline antibiotics

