3.3. Inclusion/Exclusion Criteria

3.3.1. *Inclusion criteria:*

1. Adults (≥ 18) who test positive for SARS-CoV-2 by reverse transcriptase polymerase chain reaction (RT-PCR) in an outpatient setting
2. Access to internet

3.3.2. *Exclusion criteria*

1. Symptom onset greater than 7 days prior to enrolment
2. Supplementing regularly with >500 mg vitamin C, >1000 units vitamin D, >120 mcg vitamin K (any form), or >15 mg zinc taken daily within the past month
3. Currently taking warfarin or an equivalent vitamin K antagonist anticoagulant
4. End stage chronic kidney disease
5. History of calcium oxalate kidney stones
6. Active granulomatosis (sarcoidosis, tuberculosis, lymphoma)
7. Known hypercalcemia or hypervitaminosis D

8. Currently taking either of the following antibiotics: cephalexin, tetracyclines
9. Known allergy to any investigational product, silicon dioxide, cellulose, or medium chain triglyceride oil
10. Participating in an investigational study or participation in an investigational study within the past 30 days
11. Any reason which, under the discretion of the qualified investigator or delegate, would preclude the patient from participating.

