Zinc: Zinc is one of the most abundant essential trace elements in the human body and is required for the function of several hundred enzymes and transcription factors. Zinc has long been studied in people with the common cold for the reduction of symptom severity and duration with proposed mechanisms include inhibiting binding of the rhinovirus in the nasal mucosa,⁴⁴ inhibiting proteolysis during the rhinovirus cell cycle,⁴⁵ and inhibiting rhinovirus replication.⁴⁶ Reviews of zinc administration for common cold symptoms show doses ≥ 75 mg per day outperform doses below that threshold,^{23,47} indicating a clear target dose. Of the available forms, zinc acetate has seen the largest reduction in the common cold compared to other salts⁴⁸ and will be the formulation used in this study. Whereas many common cold studies administer zinc in a lozenge form due to its local effects in the nasal cavity, rhinorrhea is less common in patients with SARS-CoV-2.⁴⁹ Based on this and the difficulty of creating a placebo lozenge, capsule form is likely not disadvantageous and the most feasible formulation for application.

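### Section 3.5 gives the zinc dose as mass of zinc acetate (8.3 mg per capsule, 75 mg per day), but the 75 mg target in section 3.4 is for zinc; made as worded, the capsules supply about 22–27 mg of zinc per day

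*Combined protocol and SAP*

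**What the plan says.** The zinc paragraph of section 3.4 gives the dose rationale: "Reviews of zinc administration for common cold symptoms show doses ≥ 75 mg per day outperform doses below that threshold", which it describes as "indicating a clear target dose". It then turns to the choice of salt, on the ground that "zinc acetate has seen the largest reduction in the common cold compared to other salts".

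Section 3.5 gives the formulation of the Vitamin C/Zinc product: "Each capsule will contain 666 mg ascorbic acid (vitamin C) and 8.3 mg of zinc acetate". The schedule is "Three capsules three times daily for 21 days", "totalling 6 g ascorbic acid and 75 mg zinc acetate per day".

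The exclusion criteria (section 3.3.2) limit participants' own supplements and count the nutrient as zinc: "or >15 mg zinc taken daily within the past month".

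For the vitamin D3 loading capsule, section 3.5 says: "Each capsule will contain 500 mg (50,000 units) cholecalciferol (vitamin D3". The K2/D drops in the same section are given as 3.125 mcg, or 125 units, of cholecalciferol per drop.

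**The concern.** A mass of zinc and a mass of zinc acetate are different quantities, because only about a third of the salt is zinc. Section 3.4 sets one threshold and then compares acetate with other salts. A threshold that applies across salts makes sense only as mass of zinc, and section 3.3.2 counts zinc the same way. Section 3.5 attaches the 75 mg figure to the salt, both per capsule and per day. No section reconciles the two or names the hydration state of the salt.

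Section 3.5 is the protocol's only formulation statement for this product. If the product is made as written there, the zinc component falls in the range that section 3.4 itself says is outperformed. A null result would then not test zinc at the dose the rationale argues for. Section 10 intends a negative result to steer patients away from an ineffective therapy, and that reading needs a known dose. So does replication or comparison with other zinc trials.

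**Working it through.** **Inputs from the protocol**
- Capsule content: 8.3 mg zinc acetate and 666 mg ascorbic acid (section 3.5).
- Schedule: three capsules three times daily, so 9 capsules per day (section 3.5).
- Stated daily totals: 75 mg zinc acetate and 6 g ascorbic acid (section 3.5).
- Target: at least 75 mg per day, stated for zinc (section 3.4).

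**Inputs assumed (standard molar masses, not in the documents)**
- Zinc 65.38; zinc acetate 183.47 anhydrous, 219.50 dihydrate.
- The hydration state is not given, so both forms are shown.

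**Step 1: reproduce the plan's totals.** 9 × 8.3 = 74.7 mg zinc acetate per day, against 75 mg stated. 9 × 666 = 5,994 mg ascorbic acid, against 6 g stated. Both agree within rounding, so the section's zinc arithmetic is consistent with itself.

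**Step 2: zinc fraction of the salt** (mass of zinc ÷ mass of salt).
- Anhydrous: 65.38 / 183.47 = 0.356.
- Dihydrate: 65.38 / 219.50 = 0.298.

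**Step 3: the two readings of 8.3 mg.**

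| Reading of 8.3 mg | Zinc per day | Share of 75 mg |
|---|---|---|
| Salt, anhydrous | 74.7 × 0.356 = 26.6 mg | 35% |
| Salt, dihydrate | 74.7 × 0.298 = 22.3 mg | 30% |
| Zinc | 9 × 8.3 = 74.7 mg | no shortfall beyond rounding |

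**Step 4: salt needed if 75 mg of zinc per day is meant.**
- Anhydrous: 75 / 0.356 ≈ 210 mg per day, or about 23 mg per capsule.
- Dihydrate: 75 / 0.298 ≈ 252 mg per day, or about 28 mg per capsule.

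**Step 5: which reading is likelier.** 75 / 9 = 8.33, so the capsule figure looks as if it was obtained by dividing the 75 mg target by nine capsules. That suggests 8.3 mg of zinc, supplied as the acetate, with the salt name in the wrong place.

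**Step 6: the vitamin D3 mass in the same section.** The drop formulation implies 3.125 / 125 = 0.025 mcg per unit. Then 50,000 × 0.025 = 1,250 mcg = 1.25 mg of cholecalciferol. The capsule line prints 500 mg, and 500 / 1.25 = 400, a 400-fold mismatch.

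**The case against.** The strongest objection is that this is only loose labelling. The number is 75 in both sections, section 3.4 gives the target and then the form, and section 3.5 can be read as that dose in that form. I think this is the likeliest explanation. But the two readings differ about threefold in zinc, and the probable intent does not correct a formulation line that a manufacturer could follow literally.

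Section 3.4 never says elemental, and its threshold comes from cited reviews that cannot be consulted here. That stands as a limit on certainty. Mass of zinc is the natural reading, and the remedy is to state the basis in section 3.4 as well. The limit in section 3.3.2 supports that reading only weakly, since it concerns participants' own supplements.

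The trial tests a four-nutrient combination, with no zinc-only arm or hypothesis, so no result could isolate zinc. The endpoint, sample size and analysis are untouched. All of this is correct, and it limits the consequence to what dose was tested and how the result may be described.

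The manufacturer's full specification and the product labels are not among the documents, so a product error cannot be established. That is also correct, and no such error is claimed.

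On vitamin D3, the capsule is identified by units, so the intended dose is clear. The 500 mg might be the mass of a diluted ingredient, at 50,000 / 500 = 100 units per mg, but the line presents it as cholecalciferol. This mismatch says nothing about how zinc is expressed; it is only a further reason to check the masses in this section.

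**Conclusion.** The inconsistency is real. Section 3.5 states as zinc acetate a dose that section 3.4 justifies as zinc, and nothing in the documents reconciles them. Followed as worded, the regimen gives about 22–27 mg of zinc per day, 30–35% of the target. If 8.3 mg was meant as zinc, there is no shortfall and only the wording is wrong. The shortfall is therefore conditional, and the documents do not show that participants were underdosed.

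The conclusion rests on standard molar masses, on both hydration states being possible, and on reading the section 3.4 threshold as mass of zinc. The comparison of the combined product with placebo is valid under either reading. The point should be settled because this is the plan's only statement of what the capsules contain. Separately, 500 mg cannot be the mass of cholecalciferol in a 50,000-unit capsule by the section's own conversion.

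**What to change.** - In section 3.5, state the content as 8.3 mg zinc (as zinc acetate) per capsule, totalling 75 mg zinc per day. Name the hydration state and give the matching salt mass: about 23 mg per capsule if anhydrous, about 28 mg if dihydrate.
- In section 3.4, say that the 75 mg threshold is mass of zinc, after confirming this in the cited reviews.
- Check both statements against the manufacturer's specification. If the product was made to salt mass, restate the dose and its rationale as about 22–27 mg zinc per day.
- In the same check, correct the vitamin D3 capsule mass to 1.25 mg (50,000 units). If 500 mg is the mass of a diluted ingredient, label it as such.

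The cost is a wording correction in two sections and one query to the manufacturer. The design and sample size do not change.

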3.6. Concomitant Medications & Stopping Rules

All concomitant medications and natural health products from enrolment to end of study (3 months) will be recorded. All information will be participant-reported. Absolute contraindications are outlined in the exclusion criteria and in section 3.5. Should a participant be placed on one of these medications or be diagnosed with one of the conditions, they will stop taking the study product. Participants may also be instructed to either temporarily or permanently discontinue the intervention if the participant does not tolerate the intervention at the discretion of study doctor or treating doctor. There are no required rescue medications for this study.

3.6.1. Standard of Care and Hospitalizations

Currently, no standard of care treatments exist for patients in the community diagnosed with COVID-19. The study team will not provide specific medical advice for participants regarding the severity of their COVID-19 symptoms aside from what is recommended by Ottawa Public Health. Study staff will follow public health guidelines and give the following procedure to participants:

“If you have any questions about COVID-19, please speak with your family doctor or contact Ottawa Public Health at [contact]. If you are in distress (significant trouble breathing, chest pain, fainting, or have a significant worsening of any chronic disease symptom), please go to the nearest emergency department or call 911.”

Participants who are hospitalized during the study will stop all study activities (i.e., treatments, questionnaires, and phone calls) and follow all recommendations given by the hospital, including treatments given post-discharge. Standard of care treatments at the hospital for COVID-19 will be the responsibility of the treating physician. If a participant receives treatments while at home, these standard of care treatments will not be withheld in any case and always supersede study interventions if there is a concern for potential interaction or side effect with the concomitant treatment. Participants will be instructed to resume study activities once they return home as tolerated. The incidence of hospitalization will be tracked using The Ottawa Hospital’s electronic medical record (EPIC) through notifications sent to the trial coordinator. Information regarding hospitalizations is also collected during phone follow-ups.

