3.7.1. Phone Calls

Follow-up calls will take place during weeks 1, 2, 3, 4, 8, and 12 to assess for outcomes, compliance, and as a general check-in with participants. Intervals will be based on the date of enrolment. Calls will be permitted to occur within 3 days of the interval date for weeks 1, 2, 3, & 4 and within 7 days for weeks 8 and 12.

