3.7.2. Measurement of Fever

Temperatures will be taken by the participant using a digital oral thermometer provided by the research staff. Participants will be instructed to wait 30 minutes after consumption of any fluids before taking their temperature. Consumption of fluids, especially cold,⁶³ can alter oral temperature readings by clinically meaningful amounts for up to 30 minutes,^{63,64} which, if unaddressed, may lead to measurement errors.

Table 1: Schedule of Events

	Time of Assessment										
	Screening (pre-enrolment)	Baseline (Prior to intervention)	Days 1-6	Day 7	Days 8-13	Day 14	Days 15-20	Day 21	Week 4	Week 8	Week 12
Eligibility	✓										
Informed Consent	✓										
Randomization		✓									
Medical History & Current Medications		✓									
Demographics		✓									
Study Intervention			✓	✓	✓	✓	✓	✓			
EQ-VAS			✓	✓	✓	✓	✓	✓			
Symptom Questionnaire			✓	✓	✓	✓	✓	✓			
EQ-5D-5L		✓		✓		✓		✓	✓	✓	✓
Phone Call Follow-Up • Concomitant Medications • Adverse Events • Hospitalizations • Delayed return to usual health				✓		✓		✓	✓	✓	✓

EQ-VAS: EuroQol Visual Assessment Scale; EQ-5D-5L: EuroQol 5-Dimension 5-Level. EQ-VAS and symptom questionnaires must be filled in on the appropriate days. A 3-day window will be allowed for EQ-5D-5L completion and phone call follow-up for the first 4 weeks. The window will increase to 5 days for weeks 8 and 12. Compliance to the intervention will be participant-reported and take place on day 21 or week 4.

Table 2: Outcome Assessment Methods

Objective	Assessment Method
Participant-reported health	EQ-VAS
Health Status	EQ-5D-5L
Symptom severity & duration of COVID-19 symptoms	Internally developed questionnaire
Incidence of delayed return to usual health	Call with participants
Incidence of Hospitalizations, including ER, acute care, and ICU admissions.	Data will be gathered through medical records and through calls with the participant
Length of Stay	
Incidence of Mortality	Data will be gathered through medical records or through obituary searches if medical records are not available

4. Study Conduct

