6.2. Data Analysis

6.2.1. Analysis Plan

6.2.1.1. Participant-Reported Overall Health & Health Status

The primary outcome analysis of participant-reported overall health will be conducted using an area under the curve approach comparing the mean difference between arms in the EQ-VAS over the 21-day intervention period. Scores will range from 0-2100 (i.e., 0-100 for 21 days) for each participant.

Health status will be measured using the crosswalk value approach. Each level from each domain of the EQ-5D-5L is aggregated to form a number defining a unique health state, with 11111 (i.e., a “1” in all domains) representing the best possible health status and 55555 (i.e., a “5” in all domains) representing the worst possible health status. Raw values will be converted to an index value out of 1. Differences in mean index values will be compared between arms at various time points over the 12-week study period. Index values will be calculated using the United States crosswalk value set provided by the EuroQol group.^{65,66}

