6.2.1.2. Symptom Severity & Duration

Symptom severity will be conducted using an area under the curve approach comparing the difference in total symptom scores over the 21-day intervention period between both arms. This gives a score range of 0-882 for each participant (i.e., 0-42 each day for 21 days). As a secondary analysis, we will compare the severity of each symptom individually using the same area under the curve approach. Scores for each symptom will range from 0-63 (i.e., 0-3 each day for 21 days). The incidence of severe symptoms (i.e., reporting a “3” for any symptom) will also be compared between arms throughout the intervention period.

The symptom duration analysis will compare the median time to symptom resolution from the start of the intervention period (or the first onset of symptoms if no symptoms were present at the start of the intervention period) up to the end of the intervention period (day 21) between both arms. Symptom resolution will be defined as a zero in all categories with no relapses.

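### Daily EQ-VAS and symptom forms stop during a hospital stay, leaving avoidable gaps in the 21-day primary total on days likely to be among a participant's worst

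*Combined protocol and SAP*

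**What the plan says.** Section 3.6.1 states that "Participants who are hospitalized during the study will stop all study activities (i.e., treatments, questionnaires, and phone calls" and then "Participants will be instructed to resume study activities once they return home as tolerated". Product, forms and calls are thus paused together, for at least the length of the stay.

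The EQ-VAS and the symptom form are both daily questionnaires. Section 3.7 ties the first to being on the intervention and the second to receiving treatment, for 21 days in each case. The note to Table 1 adds that "EQ-VAS and symptom questionnaires must be filled in on the appropriate days"; the completion windows in that note cover only the EQ-5D-5L and the calls.

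The primary analysis in 6.2.1.1 is an area under the curve of the EQ-VAS over 21 days: "Scores will range from 0-2100 (i.e., 0-100 for 21 days) for each participant". The symptom analysis in 6.2.1.2 has the same form, "comparing the difference in total symptom scores over the 21-day intervention period". Section 6.2.2 applies intention to treat and unadjusted t-tests. No section says how a day without a form is scored.

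Elsewhere the plan separates stopping product from stopping measurement. When a contraindication arises, Section 3.6 says only that "they will stop taking the study product".

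**The concern.** Following 3.6.1 exactly creates blank days in the primary outcome. The trigger is related to the outcome: 3.6.1 directs participants to emergency care for distress or significant worsening, so the unrecorded days are likely to be among the lowest EQ-VAS days and the highest symptom days. A total built from the remaining days would tend to make an admitted participant look healthier than they were. If admissions differ between arms, part of that difference would drop out of the primary comparison. The relevance missing-data section of the trial's own rationale (Section 1) names fewer hospitalizations and shorter stays among the hoped-for benefits.

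The loss is also partly avoidable. Pausing product in hospital does not require pausing self-completed forms, and the rule applies to every inpatient, including those well enough to complete them and those admitted for unrelated reasons.

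**Working it through.** The only figure the plan gives on this point is the score range, and it reproduces: 21 × 100 = 2100. That range presumes all 21 daily values.

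**Inputs from the documents.** 21 daily scores of 0-100 (6.2.1.1); 100 enrolled per arm and an effect size of 0.3, stated for a single time point at 21 days (Section 5).

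**Assumed inputs, none given in the documents.** Stay L = 7 days, all within days 1-21; hospital score V = 30; never-admitted participants score 70 every day; admitted participants score h = 50 or h = 70 on their home days; 2 v 6 admissions per 100. Scaling the average of the recorded days up to 21 is also an assumption, because the plan states no rule.

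**One participant.** True total = (21 − L)h + LV. Scaled total = 21h. Overstatement = L(h − V). A never-admitted participant totals 21 × 70 = 1470.

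| | h = 50 | h = 70 |
|---|---|---|
| True total | 14 × 50 + 7 × 30 = 910 | 14 × 70 + 7 × 30 = 1190 |
| Scaled total | 21 × 50 = 1050 | 21 × 70 = 1470 |
| Overstatement | 7 × 20 = 140 | 7 × 40 = 280 |
| True deficit v 1470 | 560 | 280 |
| Deficit kept after scaling | 420 (75%) | 0 |

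**Between arms.** Hidden difference = (difference in admissions) × L(h − V) / 100.

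- 2 v 6 admissions: 4 × 140 / 100 = 5.6 points (h = 50), or 4 × 280 / 100 = 11.2 points (h = 70).
- One extra admission: 1.4 or 2.8 points.
- Equal admissions and stays: 0.

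**Wider range.** For stays of 3-10 days and a home-to-hospital drop of 20-60 points, the overstatement runs from 3 × 20 = 60 to 10 × 60 = 600 per admitted participant. With 2 v 6 admissions that hides 2.4 to 24 points; with one extra admission, 0.6 to 6.

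**Scale.** If the SD of the 21-day total were 210-420 (assumed) and the effect size of 0.3 were applied to the total (also assumed), the planned effect would be 63-126 points.

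- 5.6 points is 5.6/126 = 4.4% to 5.6/63 = 8.9% of it.
- 11.2 points is 11.2/126 = 8.9% to 11.2/63 = 17.8%.
- The wider range is 2.4/126 = 1.9% to 24/63 = 38.1%.
- With 100 per arm the standard error is SD × √(2/100) = 29.7 to 59.4, so 5.6 points is 0.09-0.19 and 11.2 points is 0.19-0.38 standard errors.

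**The case against.** The strongest case against is that this is a defensible decision in an outpatient trial, with little effect. Inpatients are spared daily forms. ER visits, acute care and ICU admissions, length of stay and deaths are compared separately (6.2.1.4, 6.2.1.5). Research staff stay blinded until analyses are completed (4.5), so a later scoring choice would be made without knowledge of arm. Only stays overlapping days 1-21 matter, and the sickest could not complete forms anyway. All of this stands and keeps the point minor. It does not supply the missing EQ-VAS values, and blinding cannot recover data that were never collected.

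It may also be said that the 21 days could pause with the product, leaving no blank days. The calendar-day reading is not stated outright for the EQ-VAS. Table 1 schedules it by day to day 21. The symptom-duration analysis runs "up to the end of the intervention period (day 21) between both arms", and for phone calls "Intervals will be based on the date of enrolment". No section describes an extension. Even if the period did pause, the hospital days would still go unmeasured, with later days in their place.

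Two stronger readings are tempting. A reader might infer that averaging removes any effect on admissions from the primary score. That happens only in the limiting case where admitted participants feel as well at home as everyone else; low scores before admission and after discharge are still recorded, and at an assumed home score of 50 they keep 420 of the 560-point deficit. A reader might also infer that the symptom total could change sign, because a blank that adds nothing looks symptom-free. No section scores a blank as 0; in 3.7 a 0 is a recorded answer.

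Finally, the absence of a rule for blank days is a wider matter than hospital stays. The point here is the narrower one that 3.6.1 itself mandates the gaps.

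**Conclusion.** The concern holds in limited form. Section 3.6.1 builds outcome-related gaps into a 21-day total that is meant to be analysed by intention to treat, and some of those gaps could be avoided. The effect is probably small: about 5.6 to 11.2 points with 2 v 6 admissions per 100, 2.8 points or less per extra admission with a 7-day stay and a hospital score of 30, and none when admissions and stays are equal between arms. The upper end of the wider range needs long stays, a large drop in hospital, a threefold difference in admissions and a small SD all at once. Every one of these inputs is assumed. The calculation counts inpatient stays only; 3.6.1 does not say whether an emergency visit without admission also stops the forms. This is an improvement worth considering because it is inexpensive, not a flaw that undermines the primary analysis.

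**What to change.** Amend 3.6.1 so that hospitalization pauses study product and phone calls only, and participants who are able continue the daily EQ-VAS and symptom form on days 1-21. In 3.7, replace *while on the intervention* and *while receiving treatment* with *on days 1-21, whether or not product is being taken*. State how inpatients record fever, since 3.7.2 relies on a thermometer supplied to the participant.

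No extra participants or staff are needed: the forms are already self-completed on paper or in REDCap (6.3). The costs are a small daily burden for inpatients and the amendment process in 4.2.3.1, which means review by both REBs, submission to NNHPD and TPD, sign-off by the principal and qualified investigators, and team training. Gaps will remain among the sickest.
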